#### **4. Study Procedures:**

There will be a total of five study visits required for each patient. There will be one scheduled visit for baseline evaluation and four additional visits at 2 weeks, 4 weeks, 6 weeks during treatment and 8 weeks (2 weeks post stopping the treatment). The baseline visit will involve completion of a standardized intake form, which will include pertinent demographics such as age, height, weight, education level, occupation, and comorbidities of the study patient (see Table IV). Several clinical assessments will be performed at baseline as well as at each study visit to evaluate severity of neuropathy and skin perfusion as described in the table IV.

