
Baseline & each 2- week follow-up (week 2, week 4, week 6, and week 8)
 
+ 2 day visit window for each protocol related visit starting at Week 2.
	
Peripheral Neuropathy: We will evaluate Vibration Perception Threshold (VPT) Testing to evaluate large fiber neuropathy
 
We will also use Semmes-Weinstein monofilaments, and the Modified Neuropathy Disability Score. (Armstrong and Lawrence 1998) We will assess light touch and pressure sensation at nine sites on each foot using 4, 10, 26, and 60 Semmes-Weinstein gram monofilaments. (Diamond, Mueller et al. 1989) The Modified Neuropathy Disability Score is a scored clinical examination that includes Achilles deep tendon reflex, pressure, vibration sensation and temperature sensation in both feet. (Abbott, Carrington et al. 2002; Caselli, Spallone et al. 2006).
 
Pain: Visual Analogue Scale
 
Gait test: 8 sensors will be attached to the legs and lower back using comfortable straps and will be asked to walk 20 meters on a flat surface, two times. A third 20 meter walk will be performed with an additional distractive cognitive task (counting -1). The 4th test will be fast walking. Walking performance (e.g., speed, cadence, and stability) and spatio-temporal parameters of gait (e.g., velocity, stride time, gait inter-cycle variability, double support, and gait initiation) will be measured.
 
Balance test: The BalanSens™ kinematic sensor will be attached to the legs and lower back and will be used to measure the variation of subject's center of mass measured by the Romberg protocol including double stance, semi-tandem, and full-tandem tests. Patients will be asked to stand straight, feet together, hands crossed for 30 seconds, 20 seconds, and 15 seconds respectively for double stance test, semi-tandem, and full tandem tests with eyes open and closed.

Baseline and 6 weeks follow-up
	
Activity Monitoring: Spontaneous daily physical activity will be monitored in home environment for 2 days using PAMSys™
 
Removal log: participants will be asked to note the time off, time on, and reason for removal if the PAMSys™ is removed during the 2 day collection period. Refer to Activity Monitoring Log for times of use and removal.
 
Quality of life questionnaire: SF12 will be administered.

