Hypothesis 5: We also anticipate that plantar electrical stimulation will improve spontaneous daily physical activity. More specifically, the duration of walking and standing as well as activity organization (i.e. day-to-day activity fluctuation) will be improved. Spontaneous daily physical activity will be assessed using PAMSys™ designed and validated by [name] (PI) and his team with collaboration of Biosensics LLC. Participants will wear PAMSys□□ embedded in a lightweight breathable tank top worn under clothing for 2 consecutive days at baseline and each study visit (Fig 14). This device uses a combination of miniaturized kinematic sensors housed in a single portable sensor attached to the chest. It can detect body posture (sitting, standing, and lying), as well as provide an accurate assessment of periods of locomotion (e.g., walking, postural transition). The validity of this approach has been established in 3 separate pilot studies, and by benchmarking the results with independent analysis by an optical motion system.(Najafi, Aminian et al. 2002; Najafi, Aminian et al. 2003; Najafi, Wrobel et al. 2008; Najafi, Crews et al. 2010) These studies demonstrate that the PAMSys™ has an overall sensitivity of 99% for detecting the time of various postural transitions (e.g., sit-to-stand or stand-to-sit) and more than 87% sensitivity and specificity for identifying the transition type. *This fine-grained analysis of human movement represents a tremendous leap in technology over what is presently available.* Thus, this measurement technique will provide unique data, not previously acquired, on actual participation in daily life.

**Hypothesis 6:** Finally, we assumed that risk and fear of falling in the intervention group will be reduced compared to baseline and compared to sham group. To evaluate the fear of falling, we will use Fall Efficacy Scale (FES) questionnaire (Bula, Martin et al. 2006; De Bruin, Najafi et al. 2007). The risk of falling will be assessed using test timed Up&Go (Shumway-Cook, Brauer et al. 2000) as well as the duration required for rising or sitting on a chair as described by Najafi et al.(Najafi, Aminian et al. 2002)

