To determine whether gait, balance, and physical activity variables change significantly across different study visit epochs, within-subject analyses of variance (ANOVA's) will be employed. We assume that plantar electrical stimulation is helpful to improve subjects gait, balance, and physical activity. Then sensor-derived movement variables should change substantially from baseline to the end of the study for the active group with no significant change in placebo group. For example, the range of motion of COM and RCI values should be reduced and gait velocity should be increased. Next, for all continuous variables, pretreatment scores will be regressed on post-treatment scores to form residualized change scores (e.g. VPT, monofilament test, pain intensity, A1C, etc). Correlations will then be generated among these scores to determine whether changes in sensor-derived movement factors are related appropriately with increases in (clinically assessed) functional capacities and self-report measures of activities, mood, socializing, etc. ANOVA test will be used to examine significant difference between intervention and sham group at baseline for age and BMI as well as the indicated outcomes (e.g. gait, balance, VPT, ABI,. Etc). We assumed there is no significant difference between sham and intervention group at baseline for the indicated variables. The same test will be repeated for the week 12. We assumed that the outcomes of study will be improved in the intervention group compared to the sham group. Paired- sample t-test will be used to examine the retention of the electrical stimulation therapy at two weeks post stopping the therapy compared to week-12. We assumed the benefit of the electrical stimulation therapy will be retained at least for two weeks. Additional analyses will examine the degree to which early-treatment changes in cognitive variables and functional capacity variables (representing functional restoration processes) predict late-treatment changes in moving ability post plantar electrical stimulation therapy. Such analyses will also allows to elucidate the relative contributions fear of falling (assessed using FES score); and/or and range of motion (assessed using body worn sensors) made to bringing about clinically meaningful changes in gait balance control. Moderator effects will also be examined for exploratory purposes. Using gender as an example, mixed design ANOVA's will be conducted to determine whether gait and balance factors change over the course of treatment at different rates or with different patterns for men and women as well as for patients with high or low severity of neuropathy and peripheral vascular disease. We assume those who have higher peripheral vascular problem will receive maximum benefit from electrical stimulation. Additional analyses will test whether changes in gait and balance variables predict changes in clinically important outcome factors (e.g., fear of falling (FES) , quality of life (SF12), adverse events, foot ulcer, etc) depending on gender.

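### Activity monitoring is set at every visit in the Hypothesis 5 text but only at baseline and week 6 in Table IV, and Section 14 plans activity analyses at visits that Table IV does not record

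*Combined protocol and SAP*

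**What the plan says.** Two places set the schedule for the home activity recording.

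- **Specific Aim 3, Hypothesis 5:** the sensor is worn "for 2 consecutive days at baseline and each study visit".
- **Table IV:** the row headed "Baseline and 6 weeks follow-up" contains the entry "Spontaneous daily physical activity will be monitored in home environment for 2 days using PAMSys™". Table IV has a separate row for assessments at baseline and weeks 2, 4, 6 and 8 (neuropathy, pain, gait, balance). Activity is not in it.

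Section 4 fixes the number of visits: "There will be a total of five study visits required for each patient". These are a baseline visit and "four additional visits at 2 weeks, 4 weeks, 6 weeks during treatment and 8 weeks (2 weeks post stopping the treatment").

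The Analysis Plan in Section 14 then asks for four things that may involve activity:

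- a within-subject ANOVA to find "whether gait, balance, and physical activity variables change significantly across different study visit epochs";
- between-group comparisons of primary and secondary endpoints at the last treatment visit, which it places at week 12, and at two-week intervals during treatment;
- a between-group ANOVA at baseline, of which it says "The same test will be repeated for the week 12";
- a retention assessment at the visit two weeks after treatment ends, by paired t-test against week 12. No outcome is named or excluded here.

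No sentence exempts activity from any of these, and none says whether Table IV or the Hypothesis 5 text takes precedence.

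**The concern.** Both schedules are specific, so neither can be read as shorthand for the other. A site working from Table IV makes two recordings per patient. A site working from the Hypothesis 5 text makes one at every visit. Section 14 is written as though activity were available visit by visit, which only the longer schedule provides.

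Activity is the whole of Hypothesis 5. A recording that was not made at week 2, 4 or 8 cannot be recovered later, so the choice has to be settled before data collection and not at analysis. Section 3 names two recruiting centres. If they followed different texts, activity data at those weeks would be missing by centre. That is a risk of the wording; nothing in the documents shows that it happened.

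**Working it through.** **Inputs.** Visits: Section 4. Activity schedules: Hypothesis 5 text and Table IV. Enrolment of 80, 40 per group: Section 14, sample size paragraph. Each recording lasts two days in both texts.

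**Visit count.** 1 baseline + 4 later visits = 5, which agrees with the total stated in Section 4.

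**Recordings by visit.**

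| Visit (Section 4) | Hypothesis 5 text | Table IV |
|---|---|---|
| Baseline | yes | yes |
| Week 2 | yes | no |
| Week 4 | yes | no |
| Week 6 (last visit during treatment in Section 4) | yes | yes |
| Week 8 (two weeks after stopping) | yes | no |
| Per patient | 5 | 2 |
| Monitored days per patient | 5 × 2 = 10 | 2 × 2 = 4 |
| 80 patients, full attendance | 80 × 5 = 400 | 80 × 2 = 160 |

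**What each planned analysis has to work with under Table IV.**

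1. *Two-weekly between-group comparisons.* There are no activity values at weeks 2 and 4, so the comparisons before week 6 cannot be made. The week-6 comparison can.
2. *Retention test.* A pair needs a value at the end of treatment and one two weeks later. There is no week-8 recording, so 0 of 80 patients can supply a pair. This matters only if the test is meant to include activity.
3. *Within-subject ANOVA.* With k time points and n patients in a group, the degrees of freedom are k − 1 and (k − 1)(n − 1). For n = 40:
   - Hypothesis 5 schedule, k = 5: 4 and 4 × 39 = 156.
   - Table IV, k = 2: 1 and 1 × 39 = 39.

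   With two levels the analysis is a paired t-test, since F = t². A simulated data set with n = 40 confirmed this (F = 5.917, equal to t²). The ANOVA still runs, but it gives one baseline-to-week-6 contrast and says nothing about the weeks between.
4. *Between-group ANOVA at week 12.* Section 4 has no week-12 visit, so neither activity schedule supplies this value. The analysis does not separate the two schedules.

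**The case against.** The best case for leaving the plan alone has four parts.

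- **Hypothesis 5 can still be tested.** This stands. Baseline and week 6 are in both schedules, so one comparison of the arms is always available. A reader might infer that Hypothesis 5 becomes untestable or that the ANOVA cannot be run. Neither follows. Section 14 also describes the expected pattern as a change from baseline to the end of the study, which two time points can address.
- **The retention text does not name activity.** This also stands, in part. The timing of the SF-12 is given as baseline and week 6 in both Table IV and the Hypothesis 4 text, so the protocol already holds one outcome that cannot enter a week-8 test. The general retention sentence need not cover every outcome, and activity is included only by implication. The ANOVA sentence, by contrast, names activity outright.
- **Table IV is where Sections 3 and 4 send the reader for clinical assessments.** That makes it the likelier working list, but it is not a rule of precedence, and the Hypothesis 5 text is just as explicit.
- **Section 14 analyses all available data.** That governs data already collected. It does not tell a site what to collect.

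A reader might also blame Table IV for the missing week-12 activity value. The documents do not support that. The Introduction and Section 14 speak of 12 weeks, while Section 4 places its last on-treatment visit at week 6. That conflict affects both activity schedules, and those sections must be reconciled in their own right.

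**Conclusion.** The contradiction is real and lies in the current text: five recordings per patient or two, a difference of 400 − 160 = 240 two-day recordings across 80 patients. Under Table IV, activity has no values at weeks 2, 4 or 8. The between-group comparisons before week 6 are lost for activity, any retention test of activity is lost, and the ANOVA reduces to a single contrast. The baseline versus week 6 comparison is unaffected.

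This rests on three assumptions: the visits are those of Section 4; attendance is complete; and activity counts among the endpoints compared every two weeks. The last is inferred from its being a study hypothesis, because the document does not list primary and secondary endpoints. The retention consequence is conditional, as stated above.

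The point concerns one of six hypotheses. The sample size rests on vibration perception, monofilament testing and centre-of-mass sway, so its justification is not touched, and no bias has been shown. It should nonetheless be corrected, because the correction is cheap and missed recordings are permanent.

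**What to change.** Reconcile the Table IV activity row and the Hypothesis 5 text to one list of activity recordings that includes the last treatment visit, and make Section 14 match it. There are two ways to do so.

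- **Keep baseline and week 6 only.** Amend the Hypothesis 5 text. In Section 14, remove activity from the multi-visit ANOVA, the two-weekly comparisons and the retention test. State a single between-arm comparison at the last treatment visit, adjusted for the baseline recording (for example by analysis of covariance). The adjustment is not needed to cure the schedule conflict, but it uses a baseline value that is already collected, which the plan's unadjusted ANOVA does not. The cost is wording only.
- **Keep more visits.** Amend Table IV to list them. If activity is to enter the retention test, the list must include the post-treatment visit, and Section 14 should name activity there. Adding that one visit to the Table IV schedule costs 80 × 1 = 80 further recordings, two more monitored days per patient. The full five-visit schedule costs 240 further recordings, or 10 − 4 = 6 more days per patient.

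Which visit is the last treatment visit depends on resolving the separate 6-week versus 12-week conflict, so the two edits should be made together.

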#### **Table IV: Clinical Assessments**

QNPRP Protocol

Version 3 – 12 Oct 2015

Page 12 of 23

Baseline	
Medical History: This will include: duration and type of diabetes, type of diabetes medication (insulin, oral, combination therapy, diet), previous history of foot ulcers, previous history of falls, amputation (toe, foot), lower extremity bypass, lower extremity angioplasty, Coronary artery bypass surgery, cardiac angioplasty, arthritis, liver disease, osteoporosis, malignancy, and bone tumors. We will use the Kaplan co-morbidity index to record disease severity. We will use the New York Heart Association criteria to classify congestive heart failure, and the National Kidney Foundation Disease Outcomes Quality Initiative Clinical Practice Guidelines for chronic kidney disease to stage kidney disease. We will document all prescription and over-the-counter medications. We will measure height and weight to determine body mass index (BMI). We will record prescription and over-the-counter medications.

Baseline	
Social Factors: We will evaluate the following factors: marital status, years of education, type of work, tobacco history (pack years, current smoker, current use of chewing tobacco, previous smoker, no tobacco history), drug history (current, previous history, no drug history), education, occupation, and alcohol history.
 
Foot questionnaire and foot exam

Baseline Questionnaires	
Screening Test for frailty assessment: Fried Frailty Criteria: Weight loss >10 pounds in preceding year; Grip strength; Low levels of physical activity; 15 foot walk time; Exhaustion[13]
 
* Screening for cognitive problem: Folstein Mini-Mental State Exam score [15]
 
* Foot questionnaire and foot exam
 
* Barthel ADL Index
 
* Depression Assessment
 
* Fear of Falling Scale
 
* Mobility Tiredness Scale
 
* Pain Assessment Scale
 
* SF-12 (at baseline and 6 week time points)

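### Table IV as written schedules the fear-of-falling scale at baseline only and timed Up&Go at no visit, although Hypothesis 6 claims improvement from baseline and over sham on both

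*Combined protocol and SAP*

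**What the plan says.** Under Specific Aim 3, Hypothesis 6 predicts that "risk and fear of falling in the intervention group will be reduced compared to baseline and compared to sham group". For fear, "we will use Fall Efficacy Scale (FES) questionnaire". For risk, "The risk of falling will be assessed using test timed Up&Go", together with the time taken to rise from or sit on a chair. The text gives no visits for the FES or for Up&Go.

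The Analysis Plan (Section 14) mentions the FES twice: once among possible contributors to change in gait and balance, and once as an outcome whose change is to be predicted from gait and balance change. It does not name Up&Go.

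Visits are set in Section 4 and Table IV. Section 4 says "There will be a total of five study visits required for each patient": baseline and four more, the last two being "6 weeks during treatment and 8 weeks (2 weeks post stopping the treatment"). In Table IV the item "Fear of Falling Scale" stands in the baseline questionnaire row with no later time point. The same row contains "SF-12 (at baseline and 6 week time points"), the only questionnaire there marked as repeated.

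**The concern.** A claim of improvement from baseline needs at least one baseline value and one later value. A comparison with sham at the end of treatment needs a value at that visit in both arms. A site that works from Table IV would collect one fear score per patient and no Up&Go result. The fear part of Hypothesis 6, and one of its two named risk measures, would then have nothing to analyse. Neither a questionnaire score nor a timed test can be reconstructed once the visit has passed.

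**Working it through.** The plan gives no figure to reproduce. The check sets the measures needed against the measures scheduled.

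**1. Each part of the schedule**

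| Source | Content | FES | Up&Go |
|---|---|---|---|
| Table IV, baseline questionnaires | frailty, cognition, fear-of-falling scale, SF-12 and others | baseline (if this scale is the FES) | no |
| Table IV, baseline and each "week follow-up (week 2, week 4, week 6, and week 8") | neuropathy tests, pain, gait, balance | no | no |
| Table IV, baseline and 6 weeks | activity monitoring, removal log, SF-12 | no | no |
| Table IV, other assessment | fall log, patient records | no | no |
| Table IV, vascular row | perfusion measures | no | no |
| Section 4, repeated assessments | neuropathy severity and skin perfusion only | no | no |

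Of five visits, the fear scale is scheduled at 1 and Up&Go at 0. The only mention of Up&Go is in the Hypothesis 6 text.

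**2. What the text requires**

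Hypothesis 6 needs two visits for each measure: baseline and the last on-treatment visit. The Analysis Plan's use of FES change as an outcome also needs two. The minimum shortfall per patient is therefore:

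- FES: 2 − 1 = 1
- Up&Go: 2 − 0 = 2

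**3. What remains for fall risk**

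- The fall log in Table IV records falls, although its stated four-week period matches neither treatment length in the document.
- Gait inter-cycle variability, which the Specific Aim 1 text links to risk of falling, is measured at every visit.
- Chair rise/sit time can probably be derived from the PAMSys monitor, which detects postural transitions. Table IV schedules it at baseline and 6 weeks, and the Hypothesis 5 text at every visit.

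None of these measures fear of falling.

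**4. Powered comparisons**

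Section 14 sizes the trial on vibration perception threshold and monofilament testing, and on sway of the centre of mass. These tests are all in the two-weekly row of Table IV, so the gap does not touch them.

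**5. Cost of closing the minimum gap**

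Inputs: 80 patients (Sections 3 and 14), all attending, and an assumed 3 to 5 minutes per assessment.

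- Up&Go: 80 × 2 = 160
- Extra FES: 80 × 1 = 80
- Total: 160 + 80 = 240
- Staff time: 240 × 3/60 = 12 hours to 240 × 5/60 = 20 hours
- Per patient: 3 assessments, 9 to 15 minutes

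If the scale in Table IV is not the FES, the FES shortfall is 2 per patient. The total becomes 80 × 4 = 320 assessments, or 16 to 26.7 hours.

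**The case against.** The best reply is that Table IV is not a complete list of what is collected. Adverse events and weekly device-use downloads have no row in it either, and Hypothesis 6 is operative text that commits the trial to both measures. The case report forms are not in the documents and may include them. This stands to the extent that the finding is conditional: it describes what follows if Table IV is used as the schedule. It does not remove the problem. Hypothesis 6 gives no visits for the two measures, and SF-12 being marked as repeated in the same row suggests that unmarked items are not.

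A reader might infer more than the documents support, in four ways:

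- **That the Analysis Plan needs both measures at four or five visits.** Its two-weekly comparisons are for primary and secondary endpoints that the documents do not list. They cannot cover every outcome, since SF-12 is taken only at baseline and week 6. The retention test names no measure. The need for Up&Go comes from Hypothesis 6 alone.
- **That every FES analysis fails.** Where the FES is a contributor to gait and balance change, a baseline score could serve; the wording does not settle this. Only the analysis of change in FES clearly needs repeat values.
- **That no fall-risk data will exist.** The fall log, gait variability and probably chair time remain.
- **That the Table IV scale is certainly the FES.** This is a reasonable inference, but the table does not say so. If it is wrong, the FES is scheduled at no visit and the gap is larger.

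**Conclusion.** The point holds as an internal inconsistency that should be corrected before the schedule is relied on. If Table IV is followed, the fear part of Hypothesis 6 and its Up&Go component have no change from baseline and no end-of-treatment comparison with sham, and the planned analysis of FES change has no outcome data. The importance is moderate: a stated hypothesis is partly undeliverable, but its risk part is not empty and the trial's powered comparisons are intact. The conclusion rests on reading Table IV as the operative schedule. The count of one missing FES, rather than two, also assumes that the table's scale is the FES.

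**What to change.** 1. Reconcile which visit is the last on treatment. Section 4 puts it at week 6; Section 1 and the Analysis Plan describe 12 weeks of treatment.
2. In Table IV, name the fear-of-falling scale as the FES, if that is what is meant.
3. Schedule the FES and timed Up&Go at least at baseline and at the reconciled last on-treatment visit.
4. State in the Analysis Plan whether the two-weekly, early-change and retention analyses apply to these two measures, and add further visits for them only if they do.

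Steps 1, 2 and 4 are text changes for the purpose of this point. Step 3 costs the 12 to 20 staff hours worked out above, at existing visits. If step 4 calls for more, each added visit brings 80 × 2 = 160 assessments, or 8 to 13.3 hours on the same assumption of 3 to 5 minutes each.
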